	APPENDIX-C: Signature Page	197
	APPENDIX-D: Individual Data Listings	198

[figure not shown]
LIST OF ABBREVIATIONS

ADR	Adverse Drug Reaction
AE	Adverse Event/Adverse Experience
App	Application / Mobile Application
Approx.	Approximately
AK	Actinic Keratosis
CFB	Change From Baseline
CRO	Clinical Research Organization
DCF	Data Collection Form
DMP	Data Management Plan
EC	Ethics Committee
EDC	Electronic Data Collection
eDCF	Electronic Data Collection Form
FAS	Full Analysis Set
FDA	The U.S Food and Drug Administration
HCP	Healthcare Provider
HRQoL	Health Related Quality of Life
ICF	Informed Consent Form
IGA	Investigator's Global Assessment
IRB	Institutional/Independent Review Board
LSR	Local Skin Reaction
N	Number (typically refers to participants)
PI	Principal Investigator
PRO	Patient Reported Outcome
PtGA	Patient Global Assessment
QoL	Quality of Life
Qr	Questionnaire
RCT	Randomized Controlled Trial
RWE	Real World Evidence
SAE	Serious Adverse Event
SAP	Statistical analysis plan
SD	Standard Deviation
TBD	To Be Decided

PROTOCOL SUMMARY

Title:	Patient and clinician Reported Outcomes for tirbanibulin effectiveness and safety in Actinic Keratosis (PROAK).
Précis:	A prospective cohort study of patients with Actinic Keratosis (AK) in the face or scalp treated with tirbanibulin and followed for 24 weeks post treatment-initiation. Patient Reported Outcomes (PROs) and clinical profile of patients will be gathered for descriptive analyses of patient outcomes over the 24-week study observation period.
Objectives:	Evaluate PROs and clinician reported outcomes among patients with AK in the face or scalp who are prescribed tirbanibulin as part of usual care in clinical practice settings in the U.S. Primary : Evaluate PROs related to AK symptoms and impact. Secondary : Evaluate tirbanibulin treatment effectiveness, in terms of IGA of status of AK in the treated area on the face or scalp. Additional : Evaluate patient and clinician satisfaction with tirbanibulin treatment, future treatment preference, treatment adherence, and tirbanibulin safety/tolerability.
Population:	Approximately three hundred (300) patients of age ≥ 18 years at the time of initiation of treatment with tirbanibulin from clinical practices across the U.S.
Number of Sites:	Maximum of fifty sites will be recruited.
Duration of Treatment	5 days.
Study Drug & Mode of Administration	Klisyri® (1% tirbanibulin ointment); 1 single-dose packet (2.5 mg tirbanibulin in 250 mg) per administration; administered once a day for 5 consecutive days. Commercial supply of medication (5-day courses) may be supplied to clinical sites/Subjects.
Study Duration:	Approximately twenty-four months of study duration, including study set-up, 24 weeks of subject observation period and study close out, followed by study data analyses.

Schematic of Study Design

**Subject screening could be done via phone, prior to roupject's visit to the clinic; or it could be combined with Encounter # 1 (baseline data collection).*

Clinicians shall prescribe tirbanibulin (Klisri®) to eligible Subjects per own clinical judgement and manage them as they normally would, in clinical practice.

1 PROAK STUDY RATIONALE

General understanding of AK impact on different aspects of patient QoL is still evolving. A real-world study leveraging validated instruments such as Skindex-16, AKQoL and the complimentary novel EPQ (developed using modified delphi method) could help portray a broader picture of impact of AK and AK treatment on patients' QoL. Further, assessing the impact of tirbanibulin treatment on AK patient outcomes and preferences, including treatment satisfaction and future preference, in real-world community practice settings could highlight the humanistic and clinical benefits associated this tirbanibulin treatment.

2 PROAK STUDY OBJECTIVES

2.1 Study Objectives

The primary objective of the study is to evaluate PROs in terms of health-related quality of life (HRQoL) among Subjects with AK in the face or scalp who are administered tirbanibulin in real-world community practice settings in the U.S. The secondary objective is to evaluate effectiveness of tirbanibulin treatment, measured by Investigator Global Assessment (IGA) of the status of AK in the treated area on the face or scalp.

The additional study objectives include the following evaluations among study Subjects and Site Investigators:

- Subject and clinician satisfaction with tirbanibulin treatment and associated outcomes.
- Subject and clinician reported improvement in overall appearance of Subject's skin in the treated area.
- Subject and clinician reported effect/impact of LSRs.
- Subject and clinician reported future treatment preference.
- Safety and tolerability of tirbanibulin.

Note: Dermatologists are expected to predominantly constitute the Site Investigator category, while a few physician assistants and nurse practitioners may be included in the study, reflecting the routine care management of AK in community practice settings.

2.2 Key Study End Points

The primary endpoint of the study will be the PROs, in terms of self-perceived AK symptoms and impact of AK on emotional well-being and functioning as measured using Skindex-16, at Week 8.

The secondary endpoint will be the proportion of Subjects with IGA success, defined as an IGA score of completely cleared (0) or partially cleared (1) in AK status in the treated area at Week 8.

Additional endpoints of the study will include (not exclusively):

- At Week 8, Mean satisfaction scores on TSQM-9 (effectiveness, convenience and overall satisfaction) as well as ad hoc satisfaction questions.
- At Week 8, Mean satisfaction scores on ad hoc physician satisfaction questionnaire.
- At Week 8, proportion of Subjects and Investigators rating the overall appearance of the AK treated area as ‘somewhat improved or much improved.’
- At Week 8, proportion of Subjects and Investigators reporting ‘somewhat likely or very likely’ to consider tirbanibulin in the future to retreat their AK.
- Frequency of documented adverse events (AEs), serious adverse events (SAEs) and LSRs during the first 8-weeks of the study observation period.
- Investigator rating of severity of skin photodamage at Weeks 8 and 24.
- Among Subjects with prior topical treatment experience at baseline:
 - At Week 8, proportion of Subjects and Investigators respectively rating ‘convenience/ease of use’ of tirbanibulin, and/or ‘overall satisfaction’ with tirbanibulin as ‘somewhat better or much better’ in comparison to previous topical treatments to treat their AK.
 - At Week 8, proportion of Subjects and Investigators respectively rating ‘duration of skin reactions’, ‘severity of skin reactions’ and/or ‘impact on daily activities due to skin reactions’ related to tirbanibulin, as ‘somewhat better or much better’ in comparison to previous topical treatments to treat their AK.

3 STUDY DESIGN

This will be a single-arm multi-center prospective cohort study which will enroll adult patients with AK of the face or scalp who are newly initiated with tirbanibulin (Klisyri®) treatment in real-world community practices in the U.S, as part of usual care. Study subjects will be followed for up to 24 weeks post-index date (with the ‘index-date’ defined as the date of initiation of tirbanibulin). Study Site Investigators and subjects will complete electronic data collection forms (e-DCFs, or surveys) at baseline (at time of study enrollment), Week 8 and Week 24.

This study will entail provision of tirbanibulin treatment to study participants. Site Investigators will decide on who to prescribe tirbanibulin (Klisyri®) ointment (as per U.S label) as part of usual care, based on their best clinical judgment, prior to subject recruitment. The study is sponsored by Almirall, hereinafter referred to as the Sponsor. The study will be managed by Avant Health, hereinafter referred to as the Contract Research Organization (CRO).

3.1 Subject Inclusion Criteria

In order to be eligible to participate in this study, an individual must meet all of the following criteria:

- Diagnosed with AK of the face or scalp.
- Has clinically typical, visible, and discrete AK lesions.
- Considered as a potential candidate for tirbanibulin (Klisyri®) treatment to manage their AK.
- Male or female, aged 18 years and above at the time of initiation of treatment with tirbanibulin.
- Willing to avoid excessive sun or UV exposure, and/or use relevant sunscreen protection and protective clothing during the study duration.
- Able to read and write English.
- Provide consent to participate in the study.
- Willing to comply with all study procedures and be available for the duration of the study.

3.2 Subject Exclusion Criteria

An individual who meets any of the following criteria were excluded from participation in this study:

- Patients with any dermatological condition of the face or scalp that could interfere with the clinical evaluations.
- Hypertrophic AK lesions, open wounds or suspected skin cancers within close proximity of the treatment area.
- Anticipated need for in-patient hospitalization or in-patient surgery within the next 2 months.
- Patients unable to comply with the requirements of the study or patients who in the opinion of the study physician should not participate in the study.
- Patients for whom medical chart is inaccessible to physicians to complete baseline data collection.

4 STUDY SCHEDULE & PROCEDURES

Study eligible patients who are considered as candidates for tirbanibulin treatment as part of usual care AK management will be screened, consented, and recruited into the study, followed for up to 24 weeks post-index date, encompassing three distinct data collection encounters. With 'T' being the index date of tirbanibulin treatment initiation, the baseline data collection (from both Site Investigators and Subjects) may transpire anytime between T= -2 weeks post-index date and T= +7 days post-index date; the 8-week follow-up data collection (Study Encounter # 2; from both Site Investigators and Subjects) will happen at T=8 weeks post-index date \pm 7 days; and 24-week follow-up data collection (Study Encounter #3; from both Site Investigators and Subjects) will happen at T=24 weeks post-index date \pm 14 days. Index date is the planned date of first application/initiation of tirbanibulin treatment, after the subject was prescribed the tirbanibulin. Different data elements will be collected from Site Investigators and from study Subjects at these data collection encounters, as outlined below.

The schedule of events is summarized in Appendix A.

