4 STUDY DESIGN

This will be a single-arm multi-center prospective cohort study which will enroll adult patients with AK of the face or scalp who are newly initiated with tirbanibulin (Klisyri®) treatment in real-world community practices in the U.S, as part of usual care. Study subjects will be followed for up to 24 weeks post-index date (with the ‘index-date’ defined as the date of initiation of

tirbanibulin). Study Site Investigators and subjects will complete electronic data collection forms (e-DCFs, or surveys) at baseline (at time of study enrollment), Week 8 and Week 24.

This study will entail provision of tirbanibulin treatment to study participants. Site Investigators will decide on who to prescribe tirbanibulin (Klisyri®) ointment (as per U.S label) as part of usual care, based on their best clinical judgment, prior to subject recruitment. The study is sponsored by Almirall, hereinafter referred to as the Sponsor. The study will be managed by Avant Health, hereinafter referred to as the Contract Research Organization (CRO).

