5 STUDY MEDICATION

The study protocol will require identification and selection of patients considered as candidates for a specific medication, namely, tirbanibulin (Klisyri®), as part of usual care. In this context, the study medication will be tirbanibulin (Klisyri®). Clinicians at individual sites (referred to as ‘Site Investigators’) shall provide the commercial supply of tirbanibulin (Klisyri®) to eligible study Subjects.

Tirbanibulin has an evolving market access in the U.S, with payers reimbursing for the commercial prescriptions on a restricted basis. Selection of only the patients who are able to fill the prescription for reimbursed tirbanibulin may not be representative of individuals who might be candidates for tirbanibulin in the U.S; this may impact the generalization of the study results. To avoid this potential selection bias and improve the prospect of generalization of study results, the commercial supply of tirbanibulin (Klisyri®) will be supplied to Site Investigators for the 5-day treatment episode for each of their Subjects.

Per FDA prescribing information, the recommended dosage of Klisyri® (tirbanibulin ointment 1%) is 1 single-dose packet (2.5 mg tirbanibulin in 250 mg) per application, for 5 consecutive days. The Site Investigators will prescribe tirbanibulin to patients per their clinical judgement. Correspondingly, tirbanibulin prescribed dose and frequency will be captured as part of study data collection.

The first dose of tirbanibulin may be administered by the subject at the clinic (under the supervision of study personnel, at baseline encounter), or at subject's home. Following the first application, Subjects will self-administer the remaining single-dose packets once daily at home for the next 4 consecutive days. Study medication should be applied each day at approximately the same time. It is preferable that study drug application is done early in the day. Subjects will be advised so that the treatment area is not touched or made wet for approximately 12 hours after application.

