7 STUDY SCHEDULE & PROCEDURES

Study eligible patients who are considered as candidates for tirbanibulin treatment as part of usual care AK management will be screened, consented, and recruited into the study, followed for up to 24 weeks post-index date, encompassing three distinct data collection encounters. With 'T' being the index date of tirbanibulin treatment initiation, the baseline data collection (from both Site Investigators and Subjects) may transpire anytime between $T = -2$ weeks post-index date and $T = +7$ days post-index date; the 8-week follow-up data collection (Study Encounter # 2; from both Site Investigators and Subjects) will happen at $T = 8$ weeks post-index date ± 7 days; and 24-week follow-up data collection (Study Encounter #3; from both Site Investigators and Subjects) will happen at $T = 24$ weeks post-index date ± 14 days. Index date is the planned date of first application/initiation of tirbanibulin treatment, after the subject was prescribed the tirbanibulin.

Different data elements will be collected from Site Investigators and from study Subjects at these data collection encounters, as outlined below.

The schedule of events is summarized in Appendix A.

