7.1 First Study Encounter / Baseline

Baseline data collection will take place at the time of subject enrollment into the study or within a few days of recruitment. The subject encounters are expected to take place during in-person subject visits to the clinic. The recruited Site Investigators and study Subjects will be sent a weblink to the eDCFs and survey respectively for their completion. Subjects will be able to access the surveys on their mobile phone, using a study-specific Mobile App.

The following data elements will be collected at baseline, from patient medical charts and/or per Site Investigator's best clinical judgement based on their recent encounter with the study subject while prescribing tirbanibulin as part of usual care and based on subject's recent past medical history:

- Demographics (e.g., age, gender).
- General clinical characteristics, as documented in medical charts (incl. blood pressure, waist circumference, height/weight measurements, comorbidities).
- AK disease characteristics (incl. AK history, IGA of severity of current skin photodamage in the AK treated area on the face or scalp (using EPQ item)).
- Past AK treatment history (used ever, and those used within the past 6 months).
- Tirbanibulin treatment characteristics (dose, frequency, date of recommendation).
- Concomitant medications (for AK and comorbidities).

The following data elements will be collected at baseline, from study Subjects, via online survey portal or a mobile app:

- Demographics (e.g., gender, race/ethnicity, education, employment/school status, living status).
- Perceptions of AK-related symptoms and impact of AK on Subject QoL, incl. emotional well-being and functioning, using Skindex-16.

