7.2 Shipment of Study medication

Following the Site Investigator's decision to prescribe tirbanibulin (Klisyri®) to study eligible patients, a commercial supply of the appropriate dose and quantity of study medication will be shipped to the attention of Site Investigator at their clinic/site. The Site Investigators will be asked to record the planned first day of administration of tirbanibulin, and this date will constitute the study 'index date', upon which the follow-up encounter timepoints (at weeks 8 & 24) will be determined.

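### The baseline Skindex-16 may be completed up to 7 days after the index date, and no Skindex-16 output separates post-dose baselines, so resolving skin reactions could count as Symptoms improvement

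*SAP*

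**What the plan says.** Protocol 7 and SAP 4 carry the same rule. In the protocol, "the baseline data collection (from both Site Investigators and Subjects) may transpire anytime between" two weeks before and seven days after the index date; the SAP wording is "may transpire anytime between T= -2 weeks post-index date and T= +7 days post-index date".

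Other text points to an earlier, pre-dose baseline. Protocol 4 and SAP 3 place data collection "at baseline (at time of study enrollment), Week 8 and Week 24". Protocol 7.1 says: "Baseline data collection will take place at the time of subject enrollment into the study or within a few days of recruitment". Under Protocol 7.2, once the decision to prescribe is made, "a commercial supply of the appropriate dose and quantity of study medication will be shipped" to the site.

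The same documents leave a route to a later one. Protocol 5 says the first dose "may be administered by the subject at the clinic (under the supervision of study personnel, at baseline encounter") or at home, and Protocol 7.1 says Site Investigators and "study Subjects will be sent a weblink to the eDCFs and survey respectively for their completion". No section orders the Subject survey ahead of the first application.

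SAP 5.1 gives the Skindex-16 only at baseline and Week 8. Appendix B sets a past-week recall. SAP 6.4 explores change from baseline descriptively, and Tables 1.7 to 1.9 attach p-values to it. The subgroups in SAP 6.3.3 and the sensitivity analyses in SAP 6.9 and 7.5 do not use baseline timing.

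The index date has two meanings. In Protocol 7.2, sites "record the planned first day of administration of tirbanibulin", and Protocol 7 and SAP 4 also call it a planned date. Protocol 4, SAP 3 and both Appendix A footnotes describe it as initiation or first administration.

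**The concern.** A change from baseline is interpretable only if baseline describes the untreated state. Here a Subject may answer during or just after the course. Items 1 to 4, the whole Symptoms domain, cover the kind of complaint that Protocol 2.1 associates with AK treatments in general, where itching and burning are listed among local skin reactions.

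If such reactions raise the baseline score and have gone by Week 8, the drop appears as benefit. The bias runs in one direction, and a single-arm study has no comparison group to reveal it. With only two Skindex-16 administrations, no other pre-treatment score can replace an affected baseline. At stake is the Symptoms change from baseline, overall and by subgroup, with its p-values. For Emotions and Functioning an effect is possible but the documents do not show one.

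**Working it through.** The plan gives no figure to reproduce: SAP 6.1 states that no sample size or power calculation was done. The checks below show what the window permits and how large the bias could be.

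**Window and recall.** Days -14 to +7 make 22 calendar days, 7 of them after the index day. With a 7-day recall, a survey on day +d looks back over d days on or after the index date. Of treatment days 0 to 4, it covers 1, 2, 3 and 4 on days +1 to +4, and all 5 from day +5. The recall share is d/7:

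- days 1-3: mean (1+2+3)/3/7 = 2/7 = 0.286
- days 1-7: mean 4/7 = 0.571

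**Scale.** Items run 0 to 6 and the domain mean is rescaled to 0-100 (SAP 5.1). One step on all four Symptoms items is 100/6 = 16.67 points; one step on a single item is 16.67/4 = 4.17 points.

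**Bias in mean Symptoms change** = f × s × w, where f is the share of post-dose baselines, s the shift in domain points and w the recall weight (1 for full exposure). Reactions are taken to have resolved by Week 8. The values of f, s and w are assumptions.

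| Case | w = 1 | w = 0.571 | w = 0.286 |
|---|---|---|---|
| f = 5%, one step on one item | 0.05 × 4.17 = 0.21 | 0.12 | 0.06 |
| f = 20%, one step on all four items | 0.20 × 16.67 = 3.33 | 1.90 | 0.95 |

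**Break-even for a 1-point bias.** With w = 1: 1/16.67 = 6% late (four items) or 1/4.17 = 24% late (one item). With w = 0.571: 10.5% or 42%.

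**Effect on the p-value.** The SAP names no test, so I used a paired normal approximation, two-sided 0.05, N = 300, no true change, and assumed SDs of change of 15, 20 and 25. The standard error is SD/√300, and the chance of p<0.05 is Φ(b/SE − 1.96) + Φ(−b/SE − 1.96) for bias b.

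| Bias (points) | SD 15 | SD 20 | SD 25 |
|---|---|---|---|
| 0.06 | 5.1% | 5.0% | 5.0% |
| 0.12 | 5.2% | 5.1% | 5.1% |
| 0.95 | 19.6% | 13.1% | 10.1% |
| 1.90 | 59.5% | 37.8% | 26.2% |
| 3.33 | 97.1% | 82.3% | 63.7% |

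The low cases leave the nominal 5% intact. The last row needs 20% late, full recall exposure and a shift on all four items together.

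**The case against.** The route to a late baseline is narrow. Surveys are set at enrolment or within a few days, encounters are expected in person, and drug ships only after the prescribing decision. A post-dose survey mainly needs a first dose at or soon after the baseline encounter together with delayed completion of the weblink. This stands: most baselines should be pre-dose.

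The mechanism is also inferred. The study's own examples of local skin reactions (Protocol 8.5.1, SAP 5.6.1) do not name itching or burning, Protocol 2.1 describes tirbanibulin's reactions as less severe, and the Skindex-16 items ask about the skin condition, so some Subjects may leave reactions out. This too stands, and it limits the likely size.

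A reader might infer three stronger claims that the documents do not support.

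- That the plan has no means of detecting on-treatment baselines. SAP Table 4.13 tabulates skin-reaction grades in a Baseline column, and Table 4.14 lists baseline and onset dates by patient. The gap is that no Skindex-16 output is linked to them. Nor does that Baseline column prove that post-dose baselines were expected; it may be a reused layout.
- That the primary endpoint itself is biased. It is the Skindex-16 at Week 8, assessed descriptively, and Week 8 scores do not depend on when baseline was taken.
- That about a third of Subjects will have late baselines because 7 of 22 window days follow the index day. A share of days is not a share of Subjects.

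Finally, an uncontrolled pre-post change cannot be attributed to treatment whatever the baseline timing. That is true, but it does not justify leaving in a removable error that favours apparent improvement.

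**Conclusion.** The point holds as a gap in the analysis plan. The stated window permits post-dose Skindex-16 baselines, nothing orders the survey before the first application, and the Symptoms change from baseline and its p-values in Tables 1.7 to 1.9 mix pre- and post-dose baselines without distinction. Any resulting bias would favour apparent improvement.

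Its size is unknown. The range of 0.06 to 3.3 points rests wholly on assumed shares, shifts and recall weights, and its lower end is negligible. The point is worth correcting because the change is cheap and would show whether the issue matters. If few baselines are late, the flag supports the planned result.

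**What to change.** In SAP 6.4, 6.9 and Tables 1.7 to 1.9:

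1. Derive a flag for each baseline Skindex-16: before, on, or after the day of first application. Use the actual first-application date where held, otherwise the planned index date, and state which was used. With the planned date, delayed dosing can make a true pre-dose baseline look late.
2. Report the count and day distribution of day-0 and post-dose baselines.
3. Keep the all-available-data change from baseline required by SAP 6.3.1. Beside it, add a pre-dose-baseline result with its p-values, excluding baselines after day 0. The date alone cannot order a day-0 survey against a first dose given at the same encounter, so show day-0 surveys both included and excluded unless a time stamp settles the order.
4. Reconcile the index-date wording. State which date drives the visit windows and which drives baseline classification, across Protocol 4, 7, 7.2 and Appendix A and SAP 3, 4 and Appendix A.

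A protocol change to survey timing is probably moot, since SAP 7 and 7.4 treat the 300-patient cohort as already enrolled.

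The cost is one derived flag and one extra column or row. With no imputation (SAP 6.7), the pre-dose standard error grows by 1/√(1 − f), where f is the share excluded. At 5%, paired N falls from at most 300 to 285 and the standard error rises 2.6%; at 20%, N falls to 240 and it rises 11.8%. If day-0 surveys are also excluded, f is the combined share. The pre-dose subset may favour prompt responders, which is another reason to keep both results in view.
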